### **3.6.2 Study Withdrawal**

Upon discontinuation of study treatment, at any time without prejudice, subjects may:

- Continue study interventions (eg, examination, blood and tissue sampling radiographic assessments, questionnaires) and non-interventional study assessments (eg, medical record review, survival contacts), or
- Withdraw their consent for study interventions but continue non-interventional study assessments, or
- Withdraw their consent for both study interventions and non-interventional study assessments.

Reasons for study withdrawal will be recorded in the source documents and CRFs. As applicable, no further study procedures or assessments will be performed or study data collected. For subjects who withdraw consent, determination of survival status from public records such as government vital statistics or obituaries will be performed as allowed by local regulations. Subjects who withdraw from the study will not be replaced.

### **3.6.3 Study Completion**

The study will be considered complete if any of the following criteria apply:

- futility analysis of PFS: the trial has been declared futile by the Sponsor, or
- primary analysis of PFS: null hypothesis is not rejected, or
- primary analysis of PFS: null hypothesis is rejected for PFS and the null hypothesis is rejected for OS (or the final planned analysis for OS has been conducted).

### **3.6.4 End of Trial**

End of trial is defined as the last scheduled visit or scheduled procedure for the last subject (including Maintenance Phase assessments).

CONFIDENTIAL

Protocol XL184-313 Protocol Amendment 3.0  
Page 55 of 193

## 4 STUDY POPULATION

### 4.1 Target Population

This study will enroll subjects with previously untreated intermediate- and poor-risk advanced or metastatic RCC. Eligibility criteria for this study have been carefully considered to ensure the safety of the study subjects and to safeguard the integrity of the study results. It is imperative that subjects fully meet all inclusion criteria and none of the exclusion criteria. The Sponsor will not grant waivers to study eligibility criteria.

### 4.2 Inclusion Criteria

1. Histologically confirmed advanced (not amenable to curative surgery or radiation therapy) or metastatic (AJCC Stage IV) renal cell carcinoma with a clear-cell component, including subjects who also have a sarcomatoid feature.
2. Intermediate- or poor-risk RCC as defined by IMDC criteria ([Section 3.4](#))
3. Measurable disease per RECIST 1.1 as determined by the Investigator. Measurable disease must be outside the radiation field if radiation therapy was previously administered.
4. Shipment of archival tumor tissue (unstained slides or paraffin block) to the study central laboratory prior to randomization. The tumor tissue can be obtained from any organ except brain or bone and must have been biopsied no more than 2 years prior to the date of informed consent. Alternatively, a fresh tumor sample must be obtained and shipped to the study central laboratory prior to randomization if archival tumor tissue is unavailable or inadequate.
5. Recovery to baseline or  $\leq$  Grade 1 CTCAE v5 from toxicities related to any prior treatments, unless AE(s) are clinically nonsignificant and/or stable on supportive therapy. Examples of exceptions are subjects with Grade 2 neuropathy or alopecia who are allowed for trial participation.
6. Age eighteen years or meeting country definition of adult, whichever is older, on the day of consent.
7. Karnofsky Performance Status (KPS)  $\geq$ 70%.
8. Adequate organ and marrow function, based upon meeting all of the following laboratory criteria within 14 days prior to randomization:
  - a. Absolute neutrophil count (ANC)  $\geq$  1500/ $\mu$ L ( $\geq$  1.5 GI/L) without granulocyte colony-stimulating factor support within 2 weeks before screening laboratory sample collection.
  - b. Criterion intentionally left blank
  - c. Platelets  $\geq$  100,000/ $\mu$ L ( $\geq$  100 GI/L) without transfusion within 2 weeks before screening laboratory sample collection.

CONFIDENTIAL

Protocol XL184-313 Protocol Amendment 3.0  
Page 56 of 193

- d. Hemoglobin  $\geq 8$  g/dL ( $\geq 80$  g/L) without transfusion within 1 week before screening laboratory sample collection and no clinical evidence of bleeding.
- e. Alanine aminotransferase (ALT) and aspartate aminotransferase (AST)  $\leq 3 \times$  ULN.
- f. Total bilirubin  $\leq 1.5 \times$  ULN (with the exception that total bilirubin for subjects with Gilbert's disease  $\leq 3 \times$  ULN).
- g. Serum creatinine  $\leq 1.5 \times$  ULN or calculated creatinine clearance  $\geq 40$  mL/min ( $\geq 0.67$  mL/sec) using the Cockcroft-Gault equation (see [Table 5-3](#) for Cockcroft-Gault formula).
- h. Urine protein-to-creatinine ratio (UPCR)  $\leq 1$  mg/mg ( $\leq 113.2$  mg/mmol), or 24-h urine protein  $\leq 1$  g.

9. Capable of understanding and complying with the protocol requirements and must have signed the informed consent document prior to any screening assessments except those procedures performed as standard of care within the screening window.

10. Sexually active fertile subjects and their partners must agree to use highly effective methods of contraception (defined in [Appendix D](#)) during the course of the study and for 5 months for women, and 7 months for men, after the last dose of study treatment. A barrier contraceptive method (eg, condom) is also required.

11. Female subjects of childbearing potential must not be pregnant at screening. Female subjects are considered to be of childbearing potential unless one of the following criteria are met: documented permanent sterilization (hysterectomy, bilateral salpingectomy, or bilateral oophorectomy) or documented postmenopausal status (defined as 12 months of amenorrhea in a woman  $> 45$  years-of-age in the absence of other biological or physiological causes. In addition, females  $< 55$  years-of-age must have a serum follicle stimulating hormone (FSH) level  $> 40$  mIU/mL to confirm menopause). Note: Documentation may include review of medical records, medical examination, or medical history interview by study site staff.

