  - ii. Any condition requiring systemic treatment with either corticosteroids (> 10 mg daily prednisone equivalent) or other immunosuppressive medications within 14 days of randomization.
 

*Note: Inhaled, intranasal, intra-articular, or topical steroids are permitted. Adrenal replacement steroid doses > 10 mg daily prednisone equivalent are permitted. Transient short-term use of systemic corticosteroids for allergic conditions (eg, contrast allergy) is also allowed.*
  - iii. Active infection requiring systemic treatment. Acute or chronic hepatitis B or C infection, known human immunodeficiency virus (HIV) or acquired immunodeficiency syndrome (AIDS)-related illness, or known positive test for tuberculosis infection where there is clinical or radiographic evidence of active mycobacterial infection.
  - iv. History of idiopathic pulmonary fibrosis, organizing pneumonia, drug-induced pneumonitis, idiopathic pneumonitis, or evidence of active pneumonitis on screening chest computed tomograph (CT) scan
  - v. Serious non-healing wound/ulcer/bone fracture.
  - vi. Malabsorption syndrome.
  - vii. Uncompensated/symptomatic hypothyroidism.

CONFIDENTIAL

Protocol XL184-313 Protocol Amendment 3.0  
Page 59 of 193

- viii. Moderate to severe hepatic impairment (Child-Pugh B or C) ([Appendix J](#)).
- ix. Requirement for hemodialysis or peritoneal dialysis.
- x. History of solid organ or allogeneic stem cell transplant.
- xi. Known history of COVID-19 unless the subject has clinically recovered from the disease at least 30 days prior to randomization.

7. Major surgery (eg, nephrectomy, GI surgery, removal or biopsy of brain metastasis) within 4 weeks prior to randomization. Minor surgeries within 10 days prior to randomization. Subjects must have complete wound healing from major or minor surgery before randomization. Subjects with clinically relevant ongoing complications from prior surgery are not eligible.

8. Corrected QT interval calculated by the Fridericia formula (QTcF)  $> 500$  ms per electrocardiogram (ECG) within 14 days before randomization. Furthermore, subjects with a history of additional risk factors for torsades de pointes (eg, long QT syndrome) are also excluded.

*Note: If a single ECG shows a QTcF with an absolute value  $> 500$  ms, two additional ECGs at intervals of approximately 3 min must be performed within 30 min after the initial ECG, and the average of these three consecutive results for QTcF will be used to determine eligibility*

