#### **6.6.1 Management of Hepatocellular Toxicity Associated with Cabozantinib/Placebo and Nivolumab/Ipilimumab**

Elevations of aminotransferases (ALT and AST) and bilirubin have been observed during treatment with cabozantinib, nivolumab, and ipilimumab. It is recommended that subjects with elevation of ALT, AST, and/or bilirubin have more frequent laboratory monitoring of these parameters. If possible, hepatotoxic concomitant medications should be discontinued in subjects who develop increased values of ALT, AST, or bilirubin, and other causes (eg, cancer-related, infection) should be evaluated.

CONFIDENTIAL

Protocol XL184-313 Protocol Amendment 3.0  
Page 85 of 193

The following condition requires discontinuation of all study drugs:

- Drug-related ALT or AST  $> 3 \times$  ULN in combination with total bilirubin  $> 2 \times$  ULN without reasonable other explanation, consistent with drug-induced liver injury (DILI).

[Table 6-3](#) provides suggested guidance on management of hepatotoxicity related to cabozantinib/placebo and nivolumab/ipilimumab.

In the event cabozantinib/placebo is interrupted and nivolumab/ipilimumab delayed due to an increase of serum ALT or AST  $> 3.0 \times$  ULN **or** serum total bilirubin  $>$  ULN to  $1.5 \times$  ULN, nivolumab and (if fewer than 4 ipilimumab doses have been administered and no AE has occurred that led to discontinuation of ipilimumab alone) ipilimumab should be resumed upon return of liver function tests to baseline grade, at which time cabozantinib/placebo should be resumed with a dose reduction (from either two tablets per day to one tablet per day, or one tablet per day to one tablet every other day, as appropriate).

If no additional ipilimumab is to be administered, the dose of cabozantinib/placebo should be re-escalated from one tablet per day to two tablets per day no sooner than 10 days after resumption of blinded oral therapy. Alternatively, if the subject had been taking one tablet every other day, then the dose of cabozantinib/placebo may be re-escalated to one tablet every day and, if tolerated, then to two tablets per day no sooner than 14 days thereafter.

Consult with the medical monitor to discuss further management should rechallenge be followed by any recurrence of increased liver function tests.

Dose delays should not alter the timing of other study assessments, including but not limited to tumor imaging scheduled based on W1D1 ( $\leq 3$  days after randomization).

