**Table 6-3: Suggested Management of Hepatotoxicity Associated with Study Treatment**

Severity of LFT a Elevations by Laboratory Value	Dose Modification Guidance b	Management/Follow-up Guidance
AST or ALT > ULN to 3.0 x ULN and/or total bili > ULN to 1.5 x ULN, regardless of baseline value	
 
Cabozantinib: 
 
Continue cabozantinib per protocol
 
 
 
Nivolumab /Ipilimumab: 
 
Continue therapy per protocol
 
 
 
	
 
Monitor LFTs per protocol.
 
Discontinue concomitant hepatotoxic medications, if possible.
 

AST or ALT > 3.0 x ULN to $\leq$ 5 x ULN or total bili > 1.5 x ULN to $\leq$ 3 x ULN, regardless of baseline value	
 
Cabozantinib: 
 
Interrupt cabozantinib dosing.
 
If LFTs return to baseline grade, resume cabozantinib at a reduced dose. After completion of ipilimumab regimen, re-escalate cabozantinib dose as per protocol. If no additional ipilimumab doses are to be administered, the dose of cabozantinib may be re-escalated no sooner than 10 days after re-initiation of cabozantinib.
 
See Section 6.6.1 for additional guidance.
 
 
 
Nivolumab /Ipilimumab: 
 
Delay therapy per protocol.
 
If LFTs return to baseline grade, resume therapy per protocol.
 
 
 
	
 
Monitor LFTs twice weekly or more frequently as deemed clinically necessary. 
 
If tapering off steroid therapy, monitor LFTs once weekly or more often per clinical judgmentc.
 
If LFTs return to baseline grade, resume with routine monitoring.
 
 
 
If LFT elevations persist > 3 days or worsen: 
 
Administer 0.5-1 mg/kg/day methylprednisolone or oral equivalent.
 
When LFTs return to baseline grade or CTCAE Grade <math>\leq</math> 1, taper steroids over at least 1 monthc.
 
Consider prophylactic antibiotics for opportunistic infections.
 
 
 

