ALT or AST $> 3 \times$ ULN AND total bilirubin $> 2 \times$ ULN AND no radiographic evidence of biliary obstruction	
 
• All study drugs must be discontinued.
 
	
 
• Follow the above management/follow-up guidance by grade.
 

ALT, alanine aminotransferase; AST, aspartate aminotransferase; bili, bilirubin; CTCAE, Common Terminology Criteria for Adverse Events; IV, intravenous; LFT, liver function tests; ULN, upper limit of normal

a LFTs include AST, ALT and total bilirubin.

b For brevity, the term “cabozantinib” refers to blinded oral study treatment of cabozantinib or cabozantinib-matched placebo.

c Subjects on IV steroids may be switched to an equivalent dose of oral corticosteroids (eg, prednisone) at start of tapering or earlier, once sustained clinical improvement is observed. Lower bioavailability should be taken into account when switching to the equivalent dose of oral corticosteroids.

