### 8.7.2. Analysis

All laboratory data parameters and visits will include flags for values above or below laboratory reference ranges. Toxicity grades will be assigned programmatically by applying the CTCAE v5.0 guidelines. Only results with assessment dates through the end of the standard safety observation period (see [Section 4.5](#)) will be tabulated in summary tables.

Laboratory summaries will be presented in SI units. Continuous laboratory test results will be summarized by treatment group using descriptive statistics for actual values and for changes from baseline by scheduled visit. Plots showing mean and standard error at each scheduled visit (with visits shown on x-axis) may also be presented for some laboratory parameters. For test results which are below or above the quantification level, the imputed values as described in [Appendix C](#) will be used for deriving the grade and then summarized.

Tables summarizing baseline laboratory values and the incidence of laboratory abnormalities by baseline and maximum post-baseline CTCAE grade over all records will be presented. In addition, the following summaries will also be presented:

A. Liver function abnormalities will be assessed as follows:

- Shift from baseline based on normal ranges

- Summaries of subjects meeting Hy's Law laboratory screening criteria as shown below:
  - $> 3 \times \text{ULN}$  (ALT or AST),  $> 2 \times \text{ULN}$  Total Bilirubin, and  $< 2 \times \text{ULN}$  ALP
  - $> 3 \times \text{ULN}$  (ALT or AST),  $> 2 \times \text{ULN}$  Total Bilirubin, and  $\geq 2 \times \text{ULN}$  ALP
  - $> 3 \times \text{ULN}$  (ALT or AST),  $> 2 \times \text{ULN}$  Total Bilirubin

B. For renal failure surveillance, a summary of subjects meeting renal failure laboratory screening criteria as shown below will be provided:

- Serum creatinine  $\geq 3.0 \times \text{ULN}$  and  $\geq 2.0 \times$  baseline value or
- Estimated Glomerular Filtration Rate (eGFR)  $\leq 50\%$  of the baseline value or
- eGFR  $< 30 \text{ mL/min/1.73 m}^2$  and  $\geq 25\%$  reduction from the baseline value

$$\text{eGFR} = 186 \times (\text{Creatinine in mmol per L} / 88.4)^{-1.154} \times (\text{Age})^{-0.203} \times (0.742 \text{ if female}) \times (1.210 \text{ if black}) \quad [\text{from website: } \text{https://ukidney.com/nephrology-resources/egfr-calculator}]$$

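### Entry criterion 8f admits Gilbert's subjects with bilirubin up to 3 × ULN, but Table 6-3 row 2 holds treatment from above 1.5 × ULN whatever the baseline, so an eligible subject can meet the hold rule with no change

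*Protocol*

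**What the plan says.** **Entry.** Protocol Section 4.2, criterion 8 (repeated in the synopsis), caps ALT and AST at 3 × ULN (8e). It caps total bilirubin at 1.5 × ULN, "with the exception that total bilirubin for subjects with Gilbert's disease" has a limit of 3 × ULN (8f).

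**Table 6-3** sorts subjects by laboratory value:

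- Row 1 (bilirubin above ULN to 1.5 × ULN, or ALT/AST above ULN to 3 × ULN): all drugs continue.
- Row 2 includes "total bili > 1.5 x ULN to $\leq$ 3 x ULN, regardless of baseline value". The oral drug is held, both infusions are delayed, and methylprednisolone is added if the abnormality lasts more than 3 days or worsens. When values are back at the baseline grade, infusions resume and the oral drug resumes at a lower dose, with later re-escalation.
- Row 3 (bilirubin above 3 × ULN, or ALT/AST above 5 × ULN): the first row in which discontinuation appears.
- Row 4 (ALT/AST above 3 × ULN, bilirubin above 2 × ULN, and "no radiographic evidence of biliary obstruction"): all drugs stop.

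**Section 6.6.1** requires the same all-drug stop only for a drug-related event "without reasonable other explanation, consistent with drug-induced liver injury (DILI". Its paragraph on resumption refers to treatment held for bilirubin above ULN to 1.5 × ULN. It presents Table 6-3 as a suggestion for managing treatment-related hepatotoxicity. Section 6.6 says that investigators should follow 6.6.1 for hepatocellular toxicity.

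**SAP Section 8.7.2** plans "Summaries of subjects meeting Hy's Law laboratory screening criteria as shown below". All three rows need ALT or AST above 3 × ULN with bilirubin above 2 × ULN; two of them split on ALP. None refers to the subject's baseline bilirubin.

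**The concern.** Criterion 8f is a deliberate exception: the protocol chose to enrol subjects with Gilbert's disease whose bilirubin is already above the ordinary limit. The toxicity rules that follow were written as if everyone entered at or below 1.5 × ULN. The wording of row 2 that sets the baseline aside removes the reading that would otherwise rescue it.

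Sites can therefore apply the same text in different ways to the same laboratory value. Under one reading, a subject whose liver tests have not moved has the oral drug held and then reduced, infusions delayed and possibly steroids started. Sections 6.6.3.2.1 and 7.1 then require steroids to be tapered to 10 mg/day of prednisone equivalent or less before the next infusion. Under the other reading, nothing happens. On the reporting side, the Hy's Law table is a main liver-safety output for this triplet, and some subjects will enter it with half of its definition already met at baseline.

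**Working it through.** No sample-size or event arithmetic applies. The check intersects what criteria 8e and 8f admit for a Gilbert's subject (bilirubin ≤ 3, ALT/AST ≤ 3, in multiples of ULN) with each trigger.

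| Rule | Trigger (× ULN) | Met at entry? |
|---|---|---|
| Table 6-3 row 2, bilirubin | > 1.5 to 3 | Yes, for every admitted value above 1.5 |
| Table 6-3 row 2, ALT/AST | > 3 to 5 | No |
| Table 6-3 row 3, bilirubin | > 3 | No |
| Table 6-3 row 3, ALT/AST | > 5 | No |
| Row 4 and Section 6.6.1 stop | ALT/AST > 3 and bilirubin > 2 | Bilirubin half yes if > 2; ALT/AST half no; rule not met |
| SAP Hy's Law rows | ALT/AST > 3 and bilirubin > 2 | As above; not met |

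**Row 2, baseline 2.0 × ULN, unchanged.** Since 1.5 < 2.0 ≤ 3, the row applies. The value has not left its baseline grade, so the resumption condition is satisfied at the same moment. Resumption is at a reduced dose, which in Table 6-4 means 20 mg daily instead of 40 mg. If the value simply stays where it is, the condition for steroids (more than 3 days) is also met. Section 5.7.5 requires chemistry to be reviewed before every infusion after the first, so the question returns each time. The trigger ignores baseline while the release depends on it; for this subject the row does not yield a coherent instruction.

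**All-drug stop, baseline 2.5 × ULN, ALT later 3.5 × ULN, no obstruction on imaging.** Row 4: 3.5 > 3 and 2.5 > 2, and the only exception it names is absent, so all drugs stop. Section 6.6.1: the investigator must also judge the event drug-related and without another reasonable explanation, and may regard Gilbert's disease as explaining the bilirubin. The two versions can lead to different actions. The SAP counts this subject under Hy's Law on the transaminase rise alone.

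**Bilirubin 1.2 × ULN, any subject.** Row 1 says continue. The resumption paragraph of Section 6.6.1 presupposes a hold in that range. The bilirubin hold band in the text is (1, 1.5] and in the table (1.5, 3]; they do not overlap at all. This discrepancy is not confined to Gilbert's disease.

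**The case against.** The best defence is scope. Section 6.6.1 offers Table 6-3 as a suggestion and limits it to treatment-related hepatotoxicity. A bilirubin measured before the first dose cannot be treatment-related, 6.6.1 asks for other causes to be evaluated, and Section 8.1.2 exempts values consistent with those before entry from adverse event reporting. A sensible investigator would not hold drug for an unchanged value.

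This has weight, and it is why the problem is one of ambiguity rather than certain mistreatment. It does not settle the matter. Section 6.6 tells investigators to follow 6.6.1, row 2 expressly disregards baseline, and row 4 is phrased as an obligation.

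On the two stop rules, it can be said that the table's scope already implies drug-relatedness. That narrows the gap but leaves the difference between one named exception (biliary obstruction) and any reasonable explanation. It is also fair that this difference affects any alternative cause, not only Gilbert's disease.

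On the SAP, the Hy's Law rows are labelled as screening criteria, which are meant to be inclusive, and the same section gives shifts from baseline. No formal comparison of safety between arms is planned. So the rows are not wrong, but they do not let a reader separate subjects who entered above the bilirubin cut from those who crossed it on treatment.

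**Conclusion.** The conflict between criterion 8f and Table 6-3 row 2 stands on the face of the protocol, for bilirubin above 1.5 to 3 × ULN in subjects enrolled under the Gilbert's exception. It concerns the hold, the delay and the conditional steroid step. Two further inconsistencies stand: the two versions of the all-drug stop, and the hold that 6.6.1 describes where row 1 says continue. The documents do not give the number of subjects enrolled under the exception. It is likely small, and the conclusion does not depend on it.

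Four stronger readings are not supported:

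- A reader might infer that stop rules also begin at 1.5 × ULN. They do not. On bilirubin alone, discontinuation first appears above 3 × ULN, and the combined stop needs an ALT/AST value that criterion 8e rules out at entry.
- A reader might infer that these subjects lose the ipilimumab induction. Row 2 delays infusions, and 6.6.1 provides for ipilimumab to resume if fewer than four doses have been given.
- A reader might take the 10 of 44 triplet subjects with ALT increased (Section 1.6) as showing that the stop rule will often be reached. That count carries no grade or multiple of ULN.
- A reader might see the Child-Pugh exclusion (Section 4.3, 6.f.viii) as contradicting 8f, since Appendix J gives 3 points for bilirubin above 3 mg/dL and 3 + 4 × 1 = 7 is class B. An exclusion may properly narrow an inclusion. In this example the overlap also depends on a ULN that the documents do not state: at an assumed 1.0 mg/dL, 3 × ULN is 3.0, which is not above 3.

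**What to change.** **Protocol.** Reconcile criterion 8f (Section 4.2 and synopsis), the text of Section 6.6.1, and Table 6-3 rows 1, 2 and 4, so that they state one consistent handling of subjects enrolled under the Gilbert's exception, one version of the all-drug stop, and one bilirubin range for the hold. Which thresholds and exceptions apply is for the sponsor's clinicians; none is proposed here.

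**SAP Section 8.7.2.** Flag subjects with baseline total bilirubin above 1.5 × ULN, and present each Hy's Law row by arm with and without them. For flagged subjects who meet a row, show the conjugated fraction. Protocol Table 5-2 already collects it; SAP Table 17 lists total bilirubin only.

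**Cost.** Wording in one criterion, one section and one table of the protocol, and one flag in an existing SAP output. No new assessments or data.
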